### 5.1.1 Part 1: Monotherapy Escalation

During Part 1, the dose escalation with BMS-986277 monotherapy, participants with advanced or metastatic CRC, pancreatic cancer, prostate cancer, TNBC, ovarian cancer, or urothelial carcinoma meeting eligibility criteria will be permitted to receive BMS-986277.

[figure not shown]
- Initial dose of IV BMS-986277 is 100-fold below current RD for enadenotucirev.
- IV doses at  $3 \times 10^{10}$ ,  $3 \times 10^{11}$ ,  $1 \times 10^{12}$ , and  $3 \times 10^{12}$  vp are planned.
- At each dose level, Cycle 1 of BMS-986277 will be administered as a single IV infusion (D1) before proceeding to sequential dosing (consisting of 3 doses administered on Days 15, 17, and 19). A minimum of 24 hours is required between doses of BMS-986277.
- Prophylactic medication will be administered prior to each dose of BMS-986277. Pre-hydration can be administered, unless clinically contraindicated (see details of prophylaxis in [Section 7.7.2](#)).
- The 42-day Cycle 1 in Part 1 is due to a 2-week monitoring of a single virus injection, then at Day 15 (+ 7 days) BMS-986277 will be administered as in other cycles with 3 infusions within 7 days. The DLT evaluation period will include multiple virus injections. The DLT evaluation period may be extended due to non-DLT dose delays (see [Sections 7.4.1, 7.4.2, and 7.4.3](#)).
- Participants who complete the first cycle without a DLT, who have no clinical evidence of disease progression, and are considered suitable for further treatment may receive up to 1 additional cycle of BMS-986277 with the subsequent cycle beginning no sooner than 42 days after C1D1.
- Once the safety (during the DLT evaluation) of a dose level has been established, additional participants (up to a total of 12) may be added at that dose level to further evaluate the safety, PK, and pharmacodynamic profile.

**Figure 5.1.1-1: Part 1: Monotherapy Escalation**

Dosing for the initial participants into each cohort in Part 1 will be staggered by 7 days to monitor for sentinel events (See [Figure 5.1.1-2](#)).

**Figure 5.1.1-2: Sentinel Participants in Part 1**

[figure not shown]

### 5.1.2 Part 2: Combination Escalation

- Participants will receive treatment with BMS-986277 at one of 2 dose levels (for a maximum of up to 2 cycles) in combination with nivolumab (480 mg Q4W up to 26 cycles). A minimum of 24 hours is required between doses of BMS-986277.
  - Cohort 1: BMS-986277 starting at a lower dose level than the BLRM-RD
  - Cohort 2: BMS-986277 at the BLRM-RD
  - Note: A combination with a lower, intermediate, or higher dose level of BMS-986277 may be considered if the BLRM recommends it, after consideration of all available safety, PK, and pharmacodynamic data.
- A minimum of 3 participants with low ( $< 2\%$ ) or mid ( $2\% \leq \text{CD8} < 20\%$ ) CD8 TILs are required to be evaluated at each dose level. Therefore, prior to treatment in Part 2 of the study (combination escalation of BMS-986277 in combination with nivolumab), participants will undergo tumor biopsies to determine the percentage of intratumoral CD8 cells utilizing an IHC-based assay. This assay quantitates the percentage of intratumoral CD8 cells using participant tumor samples obtained during the screening period. Specific cut-offs will be used to determine the percentage of CD8 cells within a participant's tumor (low, mid, or high). See [Section 9.8](#) of the protocol for details.
- Participants who complete the first cycle and do not have a DLT, have not had disease progression, and are considered suitable for further treatment may receive up to 1 additional cycle of BMS-986277 with the subsequent cycle beginning no sooner than 28 days after C1D1. Nivolumab may be administered for up to 26 cycles.
- Once the safety (during the DLT evaluation) of a dose level has been established, additional participants (up to a total of 12) may be added at that dose level to further evaluate the safety, PK, and pharmacodynamic profile.

[figure not shown]

**Figure 5.1.2-1: Part 2: Combination Escalation**

Dosing for the initial participants into each cohort in Part 2 will be staggered by 7 days to monitor for sentinel events (see Figure 5.1.2-2).

**Figure 5.1.2-2: Sentinel Participants in Part 2**

### 5.1.3 Part 3: Expansion

[figure not shown]
Participants enrolled in Part 3 will undergo biomarker selection to determine cohort assignment and treatment. The biomarker assay used is IHC-based and quantitates percentage of intratumoral CD8+ cells using participant tumor samples obtained during the screening period. Specific cut-offs for percent CD8+ cells will be used to identify participants with either “low,” “mid,” or “high” CD8+ tumors. Participants with “low” (Cohort 1) or “mid” (Cohort 2) CD8+ tumors will be eligible for BMS-986277 in combination with nivolumab and participants with “high” (Cohort 3) CD8+ tumors will be eligible for BMS-986277 monotherapy with an option for subsequent nivolumab treatment. Please see [Section 9.8](#) of protocol for details on the biopsy requirements.

- In Part 3 Cohorts 1-2, participants will receive BMS-986277 (at the RD based on Part 2 for up to 2 cycles) in combination with nivolumab (480 mg Q4W up to 26 cycles). A minimum of 24 hours is required between doses of BMS-986277 during sequential dosing for an individual participant.

[figure not shown]
- In Part 3 Cohort 3, participants will receive BMS-986277 (at the RD based on Part 1 for up to 2 cycles). A minimum of 24 hours is required between doses of BMS-986277 during sequential dosing for an individual participant. Following 2 cycles of BMS-986277 monotherapy, participants may receive optional nivolumab treatment (480 mg Q4W) for up to 26 cycles if eligibility criteria continue to be met (see Sections 6.1 and 6.2). Participants whose disease progresses prior to receiving Cycle 2 of BMS-986277 may also receive nivolumab treatment if eligibility criteria continue to be met (see Sections 6.1 and 6.2), skipping any remaining monotherapy visits and proceeding directly to Cycle 3, optional nivolumab treatment as indicated in Table 2-5. For these participants, a minimum of 14 days will be required between the Day 1 BMS-986277 administration (Cycle 1 or Cycle 2) and the start of nivolumab administration. For participants whose disease is responding (complete or partial) per RECIST v1.1 or PCWG3 at the 8 week scan, treatment must be discussed and agreed upon with the Medical Monitor (or designee) prior to the start of the optional subsequent nivolumab treatment.
- Participants will be enrolled into 1 of 3 cohorts based on percentage of CD8 TILs:
  - Cohort 1 will treat participants with low CD8 TILs
    - ◆ Low:  $CD8 < 2\%$
  - Cohort 2 will treat participants with mid CD8 TILs
    - ◆ Mid:  $2\% \leq CD8 < 20\%$
  - Cohort 3 will treat participants with high CD8 TILs
    - ◆ High:  $CD8 \geq 20\%$
- Enrollment may focus on, but not be limited to, two indications per each cohort based on higher prevalence of the specific biomarker expression

Participants who complete the first cycle and do not have a DLT, have not had disease progression, and are considered suitable for further treatment may receive up to a maximum of 1 additional cycle of BMS-986277, with the subsequent cycle beginning no sooner than 28 days after C1D1. Nivolumab may be administered for up to 26 cycles as indicated per cohort.

**Figure 5.1.3-1: Part 3 Cohorts 1 and 2**

**Figure 5.1.3-2: Part 3 Cohort 3**

### 5.1.4 End of Treatment

EOT visits are defined by study part in [Section 2](#).

### 5.1.5 Safety Follow-up

Participants will enter safety follow-up when the maximum treatment permitted per protocol has been administered (2 cycles of BMS-986277 for participants treated with BMS-986277 monotherapy [Part 1 and Part 3 Cohort 3] or 26 cycles of nivolumab for participants treated with BMS-986277 and nivolumab [Part 2 and Part 3 Cohorts 1-3]) or once the participant discontinues from study treatment (eg, at EOT).

During safety follow-up, all participants will be evaluated for any new and/or ongoing AEs for at least 60 days for participants treated with BMS-986277 monotherapy and 100 days for participants treated with BMS-986277 and nivolumab after the last dose of study treatment. All AEs considered related to study treatment must be followed to resolution, return to baseline or when deemed irreversible as indicated in [Sections 9.2](#) and [9.2.3](#). Although AE reporting is not required following the start of subsequent anti-cancer therapies, assessments at safety follow-up visits should continue and events considered related to study treatment reported. Note that participants treated with BMS-986277 monotherapy (Part 1 and Part 3 Cohort 3) will be required to attend safety follow-up visits 1 and 2. Participants treated with BMS-986277 and nivolumab (Part 2 and Part 3 Cohorts 1-3) will be required to attend all 3 safety follow-up visits.

Safety follow-up visit 1 (FU1) should occur 30 days from the last dose ( $\pm 7$  days) or may be performed on the date of discontinuation. Safety follow-up visit #2 (FU2) occurs approximately 60 days ( $\pm 7$  days) from last dose of study drug. Safety follow-up visit #3 (FU3) occurs approximately 100 days ( $\pm 7$  days) from last dose of study drug. Safety follow-up visits must be conducted in person.

During FU1 and FU2, participants will also be evaluated for viral shedding. If virus is detected during FU2, samples should continue to be collected at least every 30 days until virus is no longer detected.

All participants will be required to complete the safety follow-up visits as indicated in [Table 2-6](#) or [Table 2-7](#) regardless of whether or not they start new anti-cancer treatment, except those participants who withdraw consent for study participation.

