**Table 2-2: On-Treatment Assessment Schedule (Monotherapy Dose Escalation - BMS-986277 [Part 1])(CA034001)**

Procedure a	Cycle 1 (42 days: 14 day lead-in period + 28 days) b				Cycle 2 (28 days) b				EOT c	Notes
	D1	D8 ( $\pm$ 3 days)	D15 d,e , D17 e , D19 e	D29 and D36 ( $\pm$ 3 days)	D1 ( $\pm$ 3 days)	D3 e and D5 e	D8 ( $\pm$ 3 days)	D15 and D22 ( $\pm$ 3 days)		
BMS-986277 Administration f	X		X		X	X				Participants will receive BMS-986277 at 1 of 4 different concentrations. Participants must be observed for at least 4 hours following the completion of BMS-986277 infusion due to the potential risk of and to monitor for infusion reactions. See Section 7.1.3.1 .

Abbreviations: AE = adverse event; C = cycle; CT = computed tomography; D = day; DLT = dose-limiting toxicity; ECG = electrocardiogram; ECOG = Eastern Cooperative Oncology Group; eCRF = electronic case report form; EOT = end of treatment; FU = follow-up; HCG = human chorionic gonadotropin; IMG = immunogenicity; IRT = interactive response technology; MRI = magnetic resonance imaging; PCWG3 = Prostate Cancer Clinical Working Group 3; PE = physical examination; PK = pharmacokinetic; Q4W = every 4 weeks; SAE = serious adverse event; SOC = standard of care; TNBC = triple-negative breast cancer; TSH = thyroid stimulating hormone; WOCBP = women of childbearing potential

- a Some of the assessments referred to in this section may not be captured as data in the eCRF. They are intended to be used as safety monitoring by the treating physician. Additional testing or assessments may be performed as clinically necessary or where required by institutional or local regulations.
- b Participants who complete the first cycle and do not have a DLT, have not had clinical evidence of disease progression, and are considered suitable for further treatment may receive up to 1 additional cycle of BMS-986277 with Cycle 2 beginning no sooner than 42 days after C1D1.
- c EOT visit is at C2D28 or at the time of study treatment discontinuation. If within 7 days prior to FU Visit 1, the EOT visit may be skipped and FU Visit 1 should be completed and include all EOT biomarker samples.
- d Up to + 7 day dosing for C1D15.

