**Table 2-6: Follow-Up Assessments (Monotherapy - BMS-986277 Only [Part 1 and Part 3 Cohort 3])(CA034001)**

Procedure	30-Day Safety Follow Up Visit 1 ( $\pm$ 7 days)	60-Day Safety Follow Up Visit 2 ( $\pm$ 7 days)	Survival Follow-Up Visits ( $\pm$ 14 days)	Notes
Safety Assessments				
Targeted PE	X	X		To assess for potential late emergent study drug related issues.
Vital Signs	X	X		
AE Assessment	X	X		To be collected through 60 days after last dose of BMS-986277 or start of subsequent anti-cancer therapy, whichever occurs earlier.
SAE Assessment	X	X		To be collected through 60 days after last dose of BMS-986277 regardless of start of subsequent anti-cancer therapy.
[REDACTED]	■	■		
Document Subsequent Cancer Therapy	X	X	Every 3 months	
ECG	Only if not assessed at EOT visit			
Laboratory Tests	X	X		On site/local laboratory testing; CBC w/differential, LFTs, BUN, creatinine, amylase, and lipase. Repeat until normalization or return to baseline if clinically significant abnormalities.
Urinalysis	X	See Notes		Repeat until normalization or return to baseline if clinically significant abnormalities at 30 day follow-up visit.
Thyroid Function Tests	X	X		TSH with reflex testing (free T3 and T4), if applicable. See Section 9.4.5. Repeat until normalization or return to baseline if clinically significant abnormalities.
Pregnancy Test (WOCBP only)	X	X		Serum or urine pregnancy test to be performed. See Section 9.4.5.

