### **7.4 Dosage Modification**

#### **7.4.1 Dose-Limiting Toxicities**

For the purpose of guiding dose escalation, DLTs will be defined based on the incidence, intensity, and duration of AEs for which no clear alternative cause is identified. The DLT evaluation period will be 42 days (6 weeks). In the event of dose delays for reasons other than a potential DLT, the DLT evaluation period may be extended to include at least 28 days after the start of the sequential doses in Part 1 or at least 14 days after the start of Cycle 2 Day 1 sequential doses in Part 2. Participants requiring dose delays >7 days may be replaced for the purposes of DLT evaluation

but permitted to remain on study treatment unless permanent discontinuation criteria (Section 8.1) are met.

In all study parts, participants who complete the first cycle and do not have a DLT, have not had clinical evidence of disease progression, and are considered suitable for further treatment may receive up to 1 additional cycle of BMS-986277.

Additionally DLT's as defined below will require permanent discontinuation for all study participants regardless of treatment cycle.

In Parts 1 and 2, participants who discontinue due to a DLT during the DLT evaluation period, will be considered as DLT-evaluable participants. Participants who withdraw from the study during the DLT evaluation period for reasons other than a DLT may be replaced with a new participant at the same dose level. The incidence of DLT(s) during the DLT evaluation period will be used in dose escalation decisions and to define the BLRM-RD. AEs occurring after the DLT period will be considered for the purposes of defining the BLRM-RD upon agreement between the Sponsor, Medical Monitor (or designee), and investigators.

Participants experiencing a DLT will enter the safety follow-up period of the study. DLTs occurring after the 6-week DLT evaluation period for Part 1 will be accounted for in determining the BLRM-RD for the combination part.

A DLT is defined as one of the following and considered by the Investigator to be possibly, probably or definitely related to BMS-986277 and/or nivolumab.

AEs will be graded according to the NCI CTCAE v4.03, as listed below:

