a EOI = End of Infusion, This sample should be taken immediately prior to stopping the infusion (preferably less than 2 minutes prior to the end of infusion). If the end of infusion is delayed to beyond the nominal infusion duration, the collection of this sample should also be delayed accordingly.

b If within 3 days of other visits, the EOT samples may be skipped.

c If virus is detected at the 60 Day Follow-up visit, samples should continue to be collected at least every 30 days until virus is no longer detected.

Infusion duration: BMS-986277 will be administered over 5 minutes except for the  $3 \times 10^{12}$  vp dose, which will be administered over 15 minutes.

**Table 9.5-2: Pharmacokinetic (PK), Anti-Drug Antibody (ADA), and Shedding Sampling Schedule for Combination Dose Escalation (Part 2) and Combination Expansion - BMS-986277 and Nivolumab (Part 3 Cohorts 1-2)(CA034001)**

Study Day of Sample Collection	Event	Time (Relative To Start of Infusion of BMS-986277 Dose ) Hour: Min	BMS-986277 Whole Blood PK Sample	BMS-986277 Serum ADA Sample	Nivolumab Serum PK Sample	Nivolumab Serum ADA Sample	BMS-986277 Shedding Sample (urine)	BMS-986277 Shedding Sample (saliva)	BMS-986277 Shedding Sample (stool) ( $\pm$ 7 days)
C1D1, C2D1	predose	00:00	X	X			X	X	X
C1D1, C2D1	EOI a	00:15	X						
C1D1, C1D5		01:00	X						
C1D1, C1D5		02:00	X						
C1D1, C1D5		03:00	X						
C1D1, C1D5		04:00	X						
C1D1, C1D5		08:00	X						
C1D3, C2D3	predose	00:00	X				X	X	X
C1D3, C2D3	EOI a	00:15	X						
C1D5, C2D5	predose	00:00	X				X	X	X
C1D5, C2D5	EOI a	00:15	X						
C1D7, C2D7		48:00	X				X	X	X
C1D15, C2D15 b	predose	00:00	X	X	X	X c	X	X	X
C1D15, C2D15 b	EOI a	00:30			X				
C1D22, C2D22		408:00	X	X			X	X	X
C3D15 b	predose	00:00			X	X	X	X	X

**Table 9.5-2: Pharmacokinetic (PK), Anti-Drug Antibody (ADA), and Shedding Sampling Schedule for Combination Dose Escalation (Part 2) and Combination Expansion - BMS-986277 and Nivolumab (Part 3 Cohorts 1-2)(CA034001)**

Study Day of Sample Collection	Event	Time (Relative To Start of Infusion of BMS-986277 Dose ) Hour: Min	BMS-986277 Whole Blood PK Sample	BMS-986277 Serum ADA Sample	Nivolumab Serum PK Sample	Nivolumab Serum ADA Sample	BMS-986277 Shedding Sample (urine)	BMS-986277 Shedding Sample (saliva)	BMS-986277 Shedding Sample (stool) ( $\pm$ 7 days)
C3D15	EOI a	00:30			X				

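### Section 5.1.5 allows the 30-day safety visit on the day of discontinuation, contrary to Tables 2-6 and 2-7, so an early discontinuer may have no further scheduled laboratory or shedding check until about day 60 after the last dose

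*Protocol*

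**What the plan says.** Protocol Section 5.1.5 places FU1 at 30 ± 7 days from the last dose and then adds an alternative: "or may be performed on the date of discontinuation". No condition limits how soon after a dose that alternative may be used.

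The FU1 column in Tables 2-6 and 2-7 is headed "30-Day Safety Follow Up Visit 1" (± 7 days), and neither table carries the alternative. Section 5.1.5 closes by making the tables binding: "All participants will be required to complete the safety follow-up visits as indicated in" Table 2-6 or Table 2-7. Section 5.1 likewise ties shedding and antibody monitoring to the 30-day and 60-day visits.

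Three further provisions matter:

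- The second visit is fixed from the last dose: "Safety follow-up visit #2 (FU2) occurs approximately 60 days" (± 7 days).
- The end-of-treatment (EOT) visit falls at discontinuation, and Table 2-2 footnote c says: "If within 7 days prior to FU Visit 1, the EOT visit may be skipped". Tables 2-3 to 2-5 have the same footnote. For the PK, antibody and shedding samples, the Section 9.5 tables add: "If within 3 days of other visits, the EOT samples may be skipped".
- On shedding, Section 5.1.5 says: "During FU1 and FU2, participants will also be evaluated for viral shedding". Sampling continues beyond FU2 only if virus is found at FU2.

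**The concern.** Two sites can each follow the protocol and give the same participant different follow-up. One brings the participant back around day 30. The other completes FU1 on the day treatment stops and next sees the participant around day 60.

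Incidence of laboratory abnormalities is a primary endpoint (Protocol Table 4-1), and this is a first-in-human study of a replicating virus. FU1 is the only routine laboratory and shedding visit between discontinuation and FU2. If it is used up on the day of discontinuation, the month after the last dose has no scheduled look. Participants who stop soon after a dose are the ones exposed. They can include some with a dose-limiting toxicity (DLT), since Section 7.4.1 states: "Participants experiencing a DLT will enter the safety follow-up period of the study".

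**Working it through.** The documents state no figure for this gap, so there is none to reproduce. The check is visit-date arithmetic.

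**Inputs.** FU1 is at day 30 ± 7, that is days 23 to 37 (Section 5.1.5; Tables 2-6 and 2-7). FU2 is at day 60 ± 7, that is days 53 to 67 (same sources). Both count from the last dose. Let d be the days from last dose to discontinuation.

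**EOT adds no later time point.** It falls at discontinuation, so it coincides with FU1 when the alternative is used, whether or not it is formally skipped.

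**Formulas.**

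- FU1 on the day of discontinuation: gap to FU2 = (60 ± 7) − d.
- Tables followed: discontinuation to FU1 = (30 ± 7) − d.
- Tables followed: FU1 to FU2 = 60 − 30 = 30 days nominally, from 53 − 37 = 16 to 67 − 23 = 44.

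| d (days) | FU1 at discontinuation: days to FU2 | Tables: days from discontinuation to FU1 |
|---|---|---|
| 0 | 60 (53 to 67) | 30 (23 to 37) |
| 7 | 53 (46 to 60) | 23 (16 to 30) |
| 14 | 46 (39 to 53) | 16 (9 to 23) |
| 23 | 37 (30 to 44) | 7 (0 to 14) |
| 28 | 32 (25 to 39) | 2 (window may already have opened) |

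**Where participants fall.**

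- d = 0 is possible: Section 7.4.5 requires permanent discontinuation at a Grade 3 or 4 nivolumab infusion reaction.
- Progression at the first 8-week scan (day 57, on-schedule dosing): in Part 1 the last dose, C2D5, is study day 42 + 5 = 47, so d = 10 and the gap is 60 − 10 = 50 days. In combination, nivolumab on C2D15 is day 28 + 15 = 43, so d = 14 and the gap is 46 days.
- A Part 1 completer has last dose C2D5 and EOT C2D28, so d = 28 − 5 = 23. That is already the lower edge of the FU1 window, so the alternative changes little.

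**Like-for-like comparison at d = 0.** The longest unscheduled interval is 60 days against 30 nominally, and 67 against 44 at the extremes of the windows.

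**Illustration (assumptions, not document figures).** Take d = 0, visits on nominal days, and a silent abnormality of fixed duration with onset uniform over the 60 days. For 14 days' duration, visits at days 30 and 60 find it with probability 2 × 14/60 = 47%, and visits at days 0 and 60 with probability 14/60 = 23%. For 21 days the figures are 42/60 = 70% and 21/60 = 35%. This describes only someone whose results were normal at discontinuation.

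**The case against.** The strongest reply is that the clause is optional, and its natural use may be for people who stop long after their last dose. Section 8.1 generally requires discontinuation once a dosing delay exceeds 6 weeks. At d = 42 the day 23 to 37 window has already closed, and FU1 at discontinuation is then reasonable. That is a fair account of why the clause might exist, but the text does not confine it to such cases.

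Existing safeguards also stand. Section 5.1.5 follows related adverse events until they settle or are judged permanent. Section 9 keeps laboratory toxicities under local monitoring, and Tables 2-6 and 2-7 repeat clinically significant abnormal results. Adverse events are collected through 60 or 100 days (unless subsequent anti-cancer therapy starts) whatever the visit spacing. FU2 shedding sampling is untouched, so persistent shedding is still found. None of this gives a routine sample before FU2 to someone with normal results at discontinuation.

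Several stronger inferences are tempting but not supported:

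- **A flat 60-day gap for early discontinuers.** It shrinks by one day for each day between last dose and discontinuation.
- **An increase from 30 ± 7 to 67 days.** That compares a single visit window with a worst case; the tables already allow 44 days between FU1 and FU2.
- **At least 16 to 33% affected.** That range is the target for the true DLT rate, not a floor on who takes this path. In the all-low scenario of Appendix 9, Table 3, the dose selected in 89.0% of simulated trials has a 10% DLT rate. Treatment is first held while a potential DLT is assessed (Section 7.4.2), and some participants may resume (Section 7.4.4).
- **Worst ascertainment in those with the worst tolerance.** Their known toxicities are the best followed.
- **A need to relabel visits in the SAP.** Laboratory results are summarised by worst grade over a period counted in days from last dose (SAP 7.1.2, 8.6 and 8.6.10), not by visit name. SAP 7.1.2 gives 30 days for Part 1 and SAP 8.6 gives 100 days for laboratory summaries. Which governs decides whether an FU2 result counts in Part 1, but relabelling would not settle that.

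**Conclusion.** The contradiction holds. Section 5.1.5 permits an FU1 timing that Tables 2-6 and 2-7 and Section 5.1 do not, and its own last paragraph points back to the tables. Followed as written, the alternative removes the only routine laboratory and shedding visit before about day 60 for a participant who stops soon after a dose.

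The size is (60 ± 7) − d days without a scheduled assessment, set against a nominal 30-day spacing (16 to 44) between FU1 and FU2 under the tables. It matters for small d and is negligible by d = 23. The loss is limited to new, silent laboratory abnormalities and interim shedding in early discontinuers.

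This rests on FU1 actually being done on the day of discontinuation and on no unscheduled testing in between. How often that would happen cannot be determined from the documents.

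**What to change.** The sponsor should reconcile Section 5.1.5 with Section 5.1 and Tables 2-6 and 2-7 so that a single FU1 timing rule applies to every participant, including those who discontinue soon after a dose and those who discontinue after the 30 ± 7 day window has passed. Which rule to adopt is for the sponsor; the passages need to agree.

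The cost is one clause in Section 5.1.5, or a matching note in the two tables. Neither adds visits beyond those the tables already require. No change to the SAP laboratory summaries is needed for this point.
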